11.3 Direct Access to Source Data/Documents for Audits and Inspections

The Sponsor or designees may conduct auditing activities of a clinical site at any time during or after completion of the study. The Investigator will be informed of such activities.

Representatives of the FDA or other regulatory agencies, including IRB/IEC representatives, may also conduct an inspection or perform an audit of the study. The Investigator(s)/institution(s) will permit trial-related audits, IRB/IEC review, and regulatory inspection(s) by providing direct access to source data/documents and study records. If informed of such an inspection, the Investigator shall notify the Sponsor immediately. The Investigator will ensure that the inspectors and auditors have access to the clinical supplies, study site facilities, and laboratory, and that all data (including original source documentation) and all study files are available, if requested.

12.0 ETHICAL CONSIDERATIONS

This study will be conducted to be consistent with the principles that have their origin in Declaration of Helsinki and in accordance with FDA regulations (21 CFR § 11, 50, 54, 56, and 312), with ICH GCP, as well as with any applicable regulatory authority, federal, state and/or local laws and regulations.

12.1 IRB/IEC Approval

Before enrollment of patients into the study, as required by FDA regulations (21 CFR § 56), ICH GCP, applicable regulatory authority requirements, and local regulations, the current protocol, Investigator's Brochure, and ICF will be reviewed and approved by the applicable regulatory authority and/or competent IRB/IEC. A letter documenting the IRB/IEC approval must be received by the Sponsor before the initiation of the study at a clinical site. Amendments to the protocol will be subject to the same requirements as the original protocol in accordance with Section 11.1.

The Investigator, Sponsor, or their designees will submit a progress report at least once yearly to the IRB/IEC, or more frequently if required by the IRB/IEC. As soon as possible after completion or termination of the study, the Investigator will submit a final report to the IRB/IEC per the IRB/IEC requirements, and in compliance with FDA regulations, applicable regulatory authority requirements, and ICH GCP.

The Investigator, the Sponsor, or their designees shall promptly notify the IRB/IEC of any SAEs, suspected unexpected serious adverse reactions (SUSARs), or any other information that may affect the safe use of the study drug(s) during the study, per the IRB/IEC local requirements, and in compliance with FDA regulations, regulatory authority regulations, and ICH GCP.

12.2 Written Informed Consent

A freely and voluntarily written documentation of informed consent must be obtained from each patient or if the patient is an incapacitated person or a minor their legal representative before entering the study. The content and approval of the ICF must meet requirements of regulations and ICH GCP. Patients will be informed of all aspects of the study that are relevant to the patient's decision to participate, and the ICF must be presented to each patient in the language in which the patient is fluent.

Informed consent will be obtained from and documented for each patient prior to the conduct of any protocol-specific procedures. Signed and dated ICFs will be retained by the Investigator with the study records. Each patient will be given a copy of the signed and dated ICF.

Any pregnancy that occurs in a study patient or the female partner of a male study patient should be reported to the Sponsor or designee. Only if a pregnant patient or partner has signed an informed consent form for disclosure information will the Sponsor or designee be able to collect

any pregnancy surveillance information. Information on this pregnancy will be collected on the Pregnancy Surveillance Form (see Section [8.12.2](#)).

13.0 DATA HANDLING AND RECORD KEEPING

13.1 Data Collection Instruments and Source Documents

13.1.1 Study Records

During the study, the Investigator/institution should maintain adequate and accurate source documents and trial records that include all pertinent observations on each of the site's trial patients. Source data should be attributable, legible, contemporaneous, original, accurate, and complete. Changes to source data should be traceable, should not obscure the original entry, and should be explained if necessary (e.g., via an audit trail). The Investigator should ensure the accuracy, completeness, legibility, and timeliness of the data reported to the Sponsor in the CRFs and in all required reports. The Investigator/institution should, at a minimum, maintain the trial documents as specified in Essential Documents for the Conduct of a Clinical Trial (ICH E6 Section 8) and as required by the applicable regulatory requirement(s). The Investigator/institution should take measures to prevent accidental or premature destruction of these documents.

13.1.2 Data Collection Instruments

Data collection instruments (DCIs) (e.g., eCRFs, electronic clinical outcomes assessments [eCOAs], and paper forms) will be used in this study. These instruments are used to transmit the information collected during the performance of this study to the Sponsor or Sponsor's designee and regulatory authorities.

The Investigator must review the DCIs for completeness and accuracy and must approve all data, including any changes made. Furthermore, the Investigator retains full responsibility for the appropriateness and accuracy of all data collected in the DCIs.

13.2 Retention of Essential Documents

The Essential Documents contained in the clinical trial master files shall be retained for 25 years or per local and regional regulations and guidelines, whichever is longer. These documents should be retained for a longer period, however, if required by an agreement with the Sponsor. At all times, the retention must meet applicable data protection laws. It is the responsibility of the Sponsor to inform the Investigator/institution in writing as to when these documents no longer need to be retained.

The Investigator shall archive the clinical trial master file securely and in a way that ensures that it is readily available and accessible, upon request, to the regulatory authorities. Sites must inform the Sponsor in writing if documents will be disposed of per Institutional Policy.

The Investigator will contact the Sponsor before transferring or destroying any study records. The Investigator will also promptly notify the Sponsor in writing in the event of accidental loss or destruction of any study records.

13.3 Confidentiality

Patient confidentiality will be maintained per legal and regulatory requirements and ICH GCP. To comply with GCP guidelines and requirements, patient records will be reviewed during monitoring visits and audits conducted by the Sponsor, Sponsor's representatives, or health authorities. During these activities, every reasonable effort will be made to keep medical information, including patient identifying information, as confidential as possible as required by law.

Study data given to, and used by, Nektar are protected by the use of a patient identification number. The assignment of unique patient identification number to each patient IRT system enables de-identification.

Demographic identifiers that will be collected as part of Study Data include year of birth, age, gender, race, and ethnicity provided this is permitted under applicable laws. Exact date of birth and patient name/initials are not collected.

The study site is not to attach the names or other directly identifying information of the patients to any Study Data or biological samples that will be transferred to Nektar. Only pseudonymized / key-coded Study Data and biological samples will be transferred to Nektar, and only the study site will be able to connect the patient identification number to a patient's personal data.

13.4 Security Measures

Sites will employ both technical and organizational measures (such as, but not limited to, controlling access to personal patient data to only those with a need to know such data, data encryption, data anonymization and pseudonymization, and so forth) to ensure patient and patient data privacy. Sites will adhere to a "privacy by design" and "privacy by default" approach in collecting, storing, and processing personal patient data.

In the event of a breach of the security measures used by the Site to ensure patient and patient data privacy, the Site will immediately notify the Sponsor.

14.0 PUBLICATION PLAN

All data are the property of the Sponsor. Any formal presentation or publication of data from this study will be considered for joint publication by the Sponsor personnel and Investigator(s).

Any publications or abstracts arising from this study must adhere to the publication requirements set forth in the clinical trial agreement governing participation in the study. Study data shared by Nektar will not contain patient identifiable information.

The Investigator may be required to sign the clinical study report if it is to be used in a registration submission to the health authorities of some countries.

APPENDIX 1: INTERNATIONAL METASTATIC RCC DATABASE CONSORTIUM (IMDC) PROGNOSTIC CRITERIA

Adverse Prognostic Factors
Clinical
Karnofsky Performance Status < 80 Time from initial diagnosis to randomization < 1 year
Laboratory (central)^a
Hemoglobin < LLN Corrected calcium > ULN ^{b, c} Absolute neutrophil count > ULN Platelet count > ULN

LLN = lower limit of normal; ULN = upper limit of normal

- a. Based on most recent central laboratory results prior to randomization. If the central laboratory test results prior to randomization are unevaluable, the last local laboratory results prior to randomization may be used for eligibility review and IMDC score calculation (See Section 8.15).
- b. Corrected calcium (mg/dL) = measured total Ca (mg/dL) + 0.8 (4.0 - serum albumin [g/dL]), where 4.0 represents the average albumin level in g/dL.
- c. Corrected calcium (mmol/L) = measured total Ca (mmol/L) + 0.02 (40 - serum albumin [g/L]), where 40 represents the average albumin level in g/L.

Risk Group Based on Number of Adverse Prognostic Factors	
Number of Adverse Prognostic Factors Present	Risk Groups
0	Favorable
1 – 2	Intermediate
3 – 6	Poor

[Heng, 2009](#)

APPENDIX 2: PERFORMANCE STATUS CRITERIA

Karnofsky Performance Status Scale	
Percent	Description
100	Normal, no complaints, no evidence of disease.
90	Able to carry on normal activity; minor signs or symptoms of disease.
80	Normal activity with effort; some signs or symptoms of disease.
70	Cares for self, unable to carry on normal activity or to do active work.
60	Requires occasional assistance, but is able to care for most of his/her needs.
50	Requires considerable assistance and frequent medical care.
40	Disabled, requires special care and assistance.
30	Severely disabled, hospitalization indicated. Death not imminent.
20	Very sick, hospitalization indicated. Death not imminent.
10	Moribund, fatal processes progressing rapidly.
0	Dead

[Schag, 1984](#)

APPENDIX 3: CLINICAL LABORATORY TESTS

Local Clinical Laboratory Tests Obtained Prior to Study Drug Administration or Dispensation

Laboratory Tests Required for Treatment Decisions		

 • AST (SGOT) • ALT (SGPT) • Serum Creatinine • Blood urea nitrogen (BUN) 	
 • Total bilirubin • Sodium • Potassium 	
 • Pregnancy test (for WOCBP) • Any additional clinically-relevant test related to individual patient monitoring

WOCBP = women of child-bearing potential

Laboratory tests must be assessed by a local laboratory within 24 hours, or as soon as locally feasible, prior to each study drug administration or dispensation.

Clinical Laboratory Test Panel

Hematology	Chemistry	Serology (screening only)

 • Hemoglobin (Hgb) • Hematocrit (HCT) • Platelet count • White blood cell (WBC) count • Neutrophils • Lymphocytes • Monocytes • Eosinophils • Basophils 	
 • AST (SGOT) • ALT (SGPT) • Alkaline phosphatase (ALP) • Albumin • Creatinine • Calculated creatinine clearance • Calcium • Glucose (non-fasting) • Total protein (TP) • Total bilirubin • Sodium • Potassium • Chloride • CO₂ content or bicarbonate • Blood urea nitrogen (BUN) or serum urea • Lactate dehydrogenase (LDH) • Uric acid 	
 • Hepatitis B surface antigen (HBsAg) • Hepatitis C virus antibody (anti-HCV) • Human immunodeficiency virus (HIV) antibody
		Additional Labs
		
 • Creatine kinase • Serum or urine pregnancy (hCG) for WOCBP • FSH ^a • Thyroid stimulating hormone (TSH) • Free thyroxine (T4) • Free or total triiodothyronine (T3) • Lipase • Amylase • C-reactive protein (Screening only)
Coagulation		

 • Partial thromboplastin time (PTT) • Prothrombin time (PT) 		

Urinalysis	

 • Specific gravity • pH • Glucose • Protein • Bilirubin • Ketones • Leukocyte esterase • Blood • Creatinine 	For positive protein, white blood cell or blood, a microscopic examination including: 
 • Red blood cells • White blood cells • Epithelial cells • Bacteria • Crystals • Casts

For urine protein, UPCR is required at Screening, and if UPCR ≥ 1.0 [≥113 mg/mmol], measurement of 24-hour urine protein is required to confirm patient meets eligibility criteria (see Inclusion Criteria 9).

Post-randomization, UPCR or dipstick analysis is acceptable; if UPCR ≥ 2.0 [≥ 227 mg/mmol] or dipstick protein ≥ 3+, measurement of 24-hour urine protein is required

a. Post-menopausal females under the age of 55 years must have a serum follicle-stimulating hormone (FSH) level > 40 mIU/mL to confirm menopause (see Appendix 4).

APPENDIX 4: WOMEN OF CHILDBEARING POTENTIAL, DEFINITIONS AND METHODS OF CONTRACEPTION

DEFINITIONS

Women of Childbearing Potential (WOCBP)

A woman is considered fertile following menarche and until becoming postmenopausal unless permanently sterile. Permanent sterilization methods include hysterectomy, bilateral salpingectomy, and bilateral oophorectomy.

Women in the following categories are not considered WOCBP:

- Premenarchal
- Premenopausal female with 1 of the following:
 - Documented hysterectomy
 - Documented bilateral salpingectomy
 - Documented bilateral oophorectomy

Note: Documentation can come from the site personnel's review of the patient's medical records, medical examination, or medical history interview.

- Postmenopausal female
 - A postmenopausal state is defined as 12 months of amenorrhea in a woman over age 45 years in the absence of other biological or physiological causes. In addition, females under the age of 55 years must have a serum follicle-stimulating hormone (FSH) level > 40 mIU/mL to confirm menopause.

CONTRACEPTION GUIDANCE FOR FEMALE PATIENTS OF CHILDBEARING POTENTIAL

One of the highly effective methods of contraception listed below is required during study duration and until the end of relevant systemic exposure, defined as 5 months after the end of study treatment (Note: local laws and regulations may require use of alternative and/or additional contraception methods).

Highly Effective Contraceptive Methods That Are User Dependent

Failure rate of <1% per year when used consistently and correctly.^a

Combined (estrogen- and progestogen-containing) hormonal contraception associated with inhibition of ovulation^b
 
 • oral • intravaginal • transdermal

Progestogen-only hormonal contraception associated with inhibition of ovulation^b
 
 • oral • injectable

Highly Effective Methods That Are User Independent

 • Implantable progestogen-only hormonal contraception associated with inhibition of ovulation^b • Hormonal methods of contraception including oral contraceptive pills containing a combination of estrogen and progesterone, vaginal ring, injectables, implants and intrauterine hormone-releasing system (IUS)^c • Intrauterine device (IUD)^c • Bilateral tubal occlusion

 • Vasectomized partner 
A vasectomized partner is a highly effective contraception method provided that the partner is the sole male sexual partner of the WOCBP and the absence of sperm has been confirmed. If not, an additional highly effective method of contraception should be used.

 • Sexual abstinence 
Sexual abstinence is considered a highly effective method only if defined as refraining from heterosexual intercourse during the entire period of risk associated with the study drug. The reliability of sexual abstinence needs to be evaluated in relation to the duration of the study and the preferred and usual lifestyle of the patient.
 
 • It is not necessary to use any other method of contraception when complete abstinence is elected. • WOCBP patients who choose complete abstinence must continue to have pregnancy tests, as specified in Section 1.2. • Acceptable alternate methods of highly effective contraception must be discussed in the event that the WOCBP patients chooses to forego complete abstinence

NOTES:
 
 a. Typical use failure rates may differ from those when used consistently and correctly. Use should be consistent with local regulations regarding the use of contraceptive methods for patients participating in clinical studies. b. Hormonal contraception may be susceptible to interaction with the study drug, which may reduce the efficacy of the contraceptive method. Hormonal contraception is permissible only when there is sufficient evidence that the IMP and other study medications will not alter hormonal exposures such that contraception would be ineffective or result in increased exposures that could be potentially hazardous. In this case, alternative methods of contraception should be utilized. c. Intrauterine devices and intrauterine hormone releasing systems are acceptable methods of contraception in the absence of definitive drug interaction studies when hormone exposures from intrauterine devices do not alter contraception effectiveness

Unacceptable Methods of Contraception^a

- Male or female condom with or without spermicide. Male and female condoms cannot be used simultaneously
- Diaphragm with spermicide
- Cervical cap with spermicide
- Vaginal Sponge with spermicide
- Progestogen-only oral hormonal contraception, where inhibition of ovulation is not the primary mechanism of action
- Periodic abstinence (calendar, symptothermal, post-ovulation methods)
- Withdrawal (coitus interruptus).
- Spermicide only
- Lactation amenorrhea method (LAM)

a. Local laws and regulations may require use of alternative and/or additional contraception methods.

CONTRACEPTION GUIDANCE FOR MALE PATIENTS WITH PARTNER(S) OF CHILDBEARING POTENTIAL

Male patients with female partners of childbearing potential are eligible to participate if they agree to the following during the treatment and until the end of relevant systemic exposure.

- Inform any and all partner(s) of their participation in a clinical drug study and the need to comply with contraception instructions as directed by the Investigator.
- Male patients are required to use a condom for study duration and until the end of relevant systemic exposure defined as 3 months after the last dose of NKTR-214.
- Female partners of males participating in the study to consider use of effective methods of contraception until the end of relevant systemic exposure, defined as 3 months after the last dose of NKTR-214 in the male patient.
- Male patients with a pregnant or breastfeeding partner must agree to remain abstinent from penile vaginal intercourse or use a male condom during each episode of penile penetration during the treatment and until 3 months after the last dose of NKTR-214.
- Refrain from donating sperm for the duration of the study treatment and until 3 months after the last dose of NKTR-214.

COLLECTION OF PREGNANCY INFORMATION

Guidance for collection of Pregnancy Information is provided in Section [8.12.2](#).

APPENDIX 5: CORTICOSTEROID DOSE EQUIVALENTS

Equivalent Dose	Steroid
1.2 mg	Betamethasone
1.5 mg	Dexamethasone
8 mg	Methylprednisolone
8 mg	Triamcinolone
10 mg	Prednisone
10 mg	Prednisolone
40 mg	Hydrocortisone
50 mg	Cortisone

[Mager, 2003; Webb, 2005](#)

APPENDIX 6: CEREBROVASCULAR ACCIDENT ADVERSE EVENT MANAGEMENT ALGORITHM (ARM A AND ARM B)

The table below provides a management algorithm for possible signs/symptoms of cerebrovascular accident (CVA) for patients in Arm A treated with the combination of NKTR-214 with a checkpoint inhibitor and patients in Arm B receiving sunitinib or cabozantinib. This general guideline constitutes guidance to the Investigator and may be supplemented by clinical judgment of the Investigator and/or discussions with the Medical Monitor representing the Sponsor.

For unexplained neurological symptoms (such as hemiparesis, confusion, dysarthria, or visual disturbances) that may be associated with CVA:	

 • Recommend following the Advanced Cardiac Life Support (ACLS) Adult Suspected Stroke Algorithm that includes time-sensitive assessment and rtPA use guidance^a. • Perform neurological imaging with DWI MRI as soon as feasible after the initial presentation of symptoms, preferably within 24 hours, or as indicated following an acute intervention. DWI MRI is preferred, but if contraindicated, alternative imaging modalities may be used. 	
If imaging is consistent with a CVA, proceed to the following:	
1	For any new CVA event confirmed by imaging (DWI MRI preferred unless contraindicated), regardless of neurological symptoms (e.g., cryptogenic CVA), and for suspected TIA without clear alternative etiology: 
 • Discontinue study treatment for patients in Arm A receiving NKTR-214 in combination with a checkpoint inhibitor (i.e., nivolumab) and patients in Arm B receiving sunitinib or cabozantinib.
2	Neurology consultation recommended.
3	Perform pertinent laboratory assessments including coagulation (D-dimer, complete blood count with differential, serum blood urea nitrogen, and creatinine) [REDACTED] preferably by central laboratory testing. Local laboratory testing is allowed when central laboratory testing is not possible.
4	Consider cardiac echocardiogram (trans-esophageal as appropriate) to evaluate for potential source of emboli.

Abbreviations: CVA = cerebrovascular accident; DWI = diffusion-weighted imaging; MRI = magnetic resonance imaging; rtPA = recombinant tissue plasminogen activator; TIA = transient ischemic attack.

- a. ACLS-algorithms.com. Adult Stroke Algorithm, (ACLS) Advanced Cardiac Life Support [Internet]; 2021 [cited 5 May 2021]. Available from: <https://acls-algorithms.com/adult-stroke-algorithm/>.

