 - Dosing delays to allow for prolonged steroid tapers to manage drug-related adverse events are allowed. Prior to re-initiating treatment in a patient with a dosing delay lasting > 8 weeks, the Medical Monitor must be consulted and agree with the rationale for resuming therapy. Tumor assessments should continue as per protocol even if dosing is delayed. Periodic study visits to assess safety and laboratory studies should also continue every 3 weeks or more frequently if clinically indicated during such dosing delays.
- Any adverse event, laboratory abnormality, or intercurrent illness which, in the judgment of the Investigator, presents a substantial clinical risk to the patient with continued nivolumab dosing.
- Any new CVA event confirmed by imaging (diffusion-weighted imaging [DWI] MRI preferred unless contraindicated), regardless of neurological symptoms, and for suspected TIA without clear alternative etiology (see [Appendix 6](#)).

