5.14.1.2 Sunitinib Discontinuation Criteria

Treatment with sunitinib should be permanently discontinued for any of the following:

- Any requirement for more than 2 sunitinib dose reductions
- Any Grade drug-related arterial thrombosis
- Grade ≥ 3 drug-related hemorrhage or recurrent Grade 3 drug-related hemorrhage after dose reduction
- Grade 4 drug-related symptomatic venous thrombosis
- LVEF reduction $\geq 50\%$ from baseline
- Grade 4 drug-related cardiac toxicity
- Any other Grade ≥ 2 drug-related arterial or venous thromboembolic events including cerebrovascular ischemia, cardiac ischemia, or peripheral or visceral arterial ischemia
- Erythema multiforme, Stevens-Johnson syndrome, toxic epidermal necrolysis or necrotizing fasciitis
- Thrombotic microangiopathy
- Nephrotic syndrome or repeat episodes of urine protein ≥ 3 g despite dose reductions
- Angioedema due to hypersensitivity
- Two or more symptomatic episodes of hypertension despite modification of antihypertensive medication(s) and reduction of sunitinib dose
- Any drug-related LFT abnormality that meets the following criteria require discontinuation:
 - Treatment-emergent ALT or AST > 3 times ULN ($> 2 \times$ baseline AND $> 3 \times$ ULN for patients with baseline elevation)
 - Total bilirubin > 2 times ULN ($> 2 \times$ baseline AND $> 2 \times$ ULN for patients with baseline elevation) or clinical jaundice, without initial findings of cholestasis (e.g., elevated serum alkaline phosphatase) (see Section 8.10)
 - Sunitinib should be interrupted for Grade 3 or 4 drug-related hepatic adverse reactions and discontinued if there is no resolution within 7 days. Sunitinib should be permanently discontinued if a patient subsequently experiences Grade 3 or 4 changes in LFT or have other signs and symptoms of liver failure.
- Any dosing delay lasting > 8 weeks unless the Medical Monitor is consulted and agrees with the rationale for resuming therapy after a delay > 8 weeks. Note that tumor assessments should continue as per protocol even if dosing is delayed.
- Any adverse event, laboratory abnormality, or intercurrent illness which, in the judgment of the Investigator, presents a substantial clinical risk to the patient with continued sunitinib dosing.

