5.14.1.3 Cabozantinib Discontinuation Criteria

Permanently discontinue cabozantinib for patients with any of the following:

- Any requirement for more than 2 cabozantinib dose reductions (i.e., reduction to less than 20 mg)
- Acute myocardial infarction or new CVA event (including TIA) confirmed by imaging (DWI MRI preferred; refer to [Appendix 6](#))
- Any other Grade ≥ 2 drug-related arterial or venous thromboembolic events including cerebrovascular ischemia, cardiac ischemia, or peripheral or visceral arterial ischemia
- LVEF reduction $\geq 50\%$ from baseline
- Any Grade ≥ 3 hemorrhage
- Grade 4 hypertension or persistent Grade 3 hypertension despite optimal medical management and cabozantinib dose reduction
- Reversible posterior leukoencephalopathy syndrome
- Development of GI perforation or drug-related fistula
- Nephrotic syndrome or recurrent nephrotic range proteinuria (i.e., recurrent 24-hour urine protein ≥ 3 g after dose reduction)
- Any drug-related LFT abnormality that meets the following criteria requires discontinuation:
 - Treatment-emergent ALT or AST > 3 times ULN ($> 2 \times$ baseline AND $> 3 \times$ ULN for patients with baseline elevation)
 - Total bilirubin > 2 times ULN ($> 2 \times$ baseline AND $> 2 \times$ ULN for patients with baseline elevation) or clinical jaundice, without initial findings of cholestasis (e.g., elevated serum alkaline phosphatase) (see Section [8.10](#))
- Any Grade 4 drug-related adverse event or laboratory abnormality, with the following exceptions:
 - Grade 4 neutropenia ≤ 7 days
 - Grade 4 lymphopenia or leukopenia
 - Grade 4 amylase or lipase abnormalities that are not associated with symptoms or clinical manifestations of pancreatitis
 - Isolated Grade 4 electrolyte abnormalities that are not associated with clinical sequelae and are corrected with supplementation/appropriate management within 72 hours of their onset
- Any dosing delay lasting > 8 weeks unless the Medical Monitor is consulted and agrees with the rationale for resuming therapy after a delay > 8 weeks. Note that tumor assessments should continue as per protocol even if dosing is delayed.

- Any adverse event, laboratory abnormality, or intercurrent illness which, in the judgment of the Investigator, presents a substantial clinical risk to the patient with continued cabozantinib dosing.

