8.11 Adverse Events of Special Interest

The AEs listed below are considered AESIs. Regardless of the assessment of whether the AESI is serious or nonserious, all AESIs are required to follow the timeline for SAE reporting (within 24 hours as described in Section 8.7) from the sites to Nektar Drug Safety: [contact].

- CVA events (including TIA; any grade; CVA Management Guidelines are provided in [Appendix 6](#))

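### The CVA/TIA discontinuation rules disagree between Appendix 6 and the sunitinib and cabozantinib lists, and Appendix 6 puts its suspected-TIA rule under a positive-imaging condition

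*Protocol*

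**What the plan says.** Protocol 8.11 lists one adverse event of special interest: "CVA events (including TIA; any grade; CVA Management Guidelines are provided in" Appendix 6.

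Appendix 6 is titled for both arms. After the advice on imaging comes a row reading "If imaging is consistent with a CVA, proceed to the following", and the four numbered rows follow it. Row 1 covers any new CVA confirmed by imaging, with or without symptoms, "and for suspected TIA without clear alternative etiology". Its action is to discontinue study treatment in Arm A "and patients in Arm B receiving sunitinib or cabozantinib". Row 1 sets no condition on relatedness or grade. The introduction to Appendix 6 calls it guidance that clinical judgment may supplement.

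The drug lists read as follows.

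- **Arm A (5.14.1.1).** The opening paragraph sends CVA and suspected TIA to the criteria in that list, with Appendix 6 for further detail. The list stops treatment for an imaging-confirmed new CVA "regardless of neurological symptoms, and for suspected TIA without clear alternative etiology".
- **Sunitinib (5.14.1.2).** Neither CVA nor TIA is named and Appendix 6 is not cited. The nearest criteria are drug-related arterial thrombosis of any grade, drug-related hemorrhage of Grade 3 or higher, and "Any other Grade ≥ 2 drug-related arterial or venous thromboembolic events including cerebrovascular ischemia".
- **Cabozantinib (5.14.1.3).** One criterion is "Acute myocardial infarction or new CVA event (including TIA) confirmed by imaging", with a reference to Appendix 6. The list also has the Grade 2 or higher drug-related thromboembolic criterion.
- **TKI dose delay (5.13.10).** For both TKIs it repeats discontinuation for drug-related arterial thromboembolic events of Grade 2 or higher and drug-related hemorrhage of Grade 3 or higher.

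Both TKI lists end with an investigator-judgment clause for any event posing substantial clinical risk. Section 5.14.1 has a general clause for events that make continued participation contrary to the patient's interest. Neither clause depends on relatedness.

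**The concern.** Protocol 2.3.2.2 explains that CVA became an event of special interest in 2020. It names the Appendix 6 algorithm and the discontinuation criteria among the mitigations, and these are the texts that disagree.

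For an Arm B patient, the answer to whether treatment stops depends on which page the site opens. It can depend on whether the investigator calls the event related, in an open-label trial, and on which TKI the patient takes. SAP 8.3.1 tabulates ischemic cerebrovascular events leading to discontinuation by arm, so the ambiguity reaches one planned safety output.

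**Working it through.** The plan states no figure for this point, so the check sets the rules side by side and runs the same event through each. In the table, judgment means that no event-specific criterion is met and only the general investigator-judgment clauses apply.

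| Event | Appendix 6 | Arm A list (5.14.1.1) | Sunitinib list (5.14.1.2) | Cabozantinib list (5.14.1.3) |
|---|---|---|---|---|
| 1. Ischemic CVA confirmed by imaging, Grade 2 or higher, judged drug-related | Stop | Stop | Stop | Stop |
| 2. New CVA confirmed by imaging, judged not drug-related | Stop | Stop | Judgment | Stop |
| 3. Suspected TIA, imaging negative, no clear other cause, judged not drug-related | Row 1 wording: stop. Row above it: row 1 not reached | Stop | Judgment | Judgment |

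**Event 1** is the control: all texts agree.

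**Event 2** separates sunitinib from the rest. Appendix 6 names sunitinib and sets no relatedness condition. Every thrombosis, thromboembolism and hemorrhage criterion in 5.14.1.2 carries one, and 5.13.10 repeats it for arterial events and hemorrhage. Cabozantinib agrees with Appendix 6 here.

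**Event 3** separates both TKI lists from row 1 of Appendix 6 and from the Arm A list. It also shows Appendix 6 disagreeing with itself: the suspected-TIA limb needs no positive scan, but it sits below a row that a site passes only with one. The Arm A list states the same limb with no such condition.

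**Precedence.** For Arm A, 5.14.1.1 says which criteria to follow. For Arm B nothing does: 5.14.1 is worded as a requirement and points to the drug lists, while Appendix 6 names both TKIs but describes itself as guidance.

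**Size.** The documents give no CVA rate for sunitinib or cabozantinib and no expected split between them. As an assumption only, a CVA rate of 0.5% to 2% among 300 Arm B patients gives 0.005 × 300 = 1.5 to 0.02 × 300 = 6 events. Only the sunitinib events judged unrelated would fall under event 2. Imaging-negative suspected TIAs on either TKI come on top, with no figure to work from.

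**The case against.** The strongest reply is that the texts are cumulative. The sunitinib list gives reasons to stop; nowhere does it say to continue when Appendix 6 applies. Section 8.11 directs sites to Appendix 6 for every CVA or TIA on any drug, and Appendix 6 names sunitinib. On that reading event 2 is settled and 5.14.1.2 merely lacks a cross-reference. This is fair as far as it goes. It relies on Appendix 6 operating as a stopping rule, however, while Appendix 6 calls itself guidance. It also cannot settle event 3, where Appendix 6 gives two answers.

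A second reply is that the investigator can always stop treatment. That stands. A reader might infer that sunitinib stops only for drug-related events, or that relatedness alone decides; the judgment clauses in 5.14.1.2 and 5.14.1 rule that out. But discretion is not the criterion that row 1 of Appendix 6 states.

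A third reply is that Arm A, where the CVA signal arose, is already covered. That stands too: the imaging row still conflicts with 5.14.1.1, but with little practical effect.

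**Conclusion.** The inconsistency is real and lies mainly in Arm B. Stated rules for the event of special interest in Protocol 8.11 give different answers for a sunitinib CVA judged unrelated and for an imaging-negative suspected TIA on either TKI. Few patients are likely to be affected. The reason to correct it is patient safety and clear instruction to sites; no power or error-rate question arises.

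Three stronger inferences are not supported.

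- **That sites have treated the same event differently.** The wording permits this; nothing in the documents shows it.
- **That the program's CVA figures measure the problem.** The 19 of 1116 patients (1.7%) on NKTR-214 plus nivolumab, and the 4 fatal outcomes among 26 patients with events, are NKTR-214 data. They explain why CVA is monitored, but they do not count Arm B patients under an unclear rule.
- **That recurrent-CVA, exposure or general discontinuation comparisons are invalidated.** SAP 8.3.1 plans no recurrence analysis. Occurrence of a first event and its time to onset are fixed before any stopping rule acts. Discontinuation criteria already differ by drug by design. The output touched is the summary of ischemic cerebrovascular events leading to discontinuation.

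The conclusion rests on a literal reading of the Appendix 6 table and on no precedence being stated for Arm B.

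**What to change.** Reconcile 5.13.10, 5.14.1.1, 5.14.1.2, 5.14.1.3 and Appendix 6:

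- Give each drug one CVA/TIA criterion, worded the same in its own list and in Appendix 6, and say whether drug-relatedness and imaging confirmation are required.
- Cite Appendix 6 in 5.14.1.2.
- State which text governs if the two differ.
- Make the imaging row in Appendix 6 consistent with row 1, so that it is plain whether an imaging-negative suspected TIA is covered.

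The sponsor decides the clinical content; this review takes no position on which rule is right. The cost is wording in the next amendment and a memo to sites, with no added procedures or patients.
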